12.0 Withdrawal of Participants

12.1 Withdrawal Circumstances:

Participants will be allowed to withdraw from the study at any time. Those who wish to withdraw may notify the research team in writing or by telephone. Participants may also be withdrawn from the study at any time based upon investigator judgement. Finally, in the event that a participant has a serious adverse event that is deemed related to the study medication and/or procedures by either the external or internal medical monitor ([name] and [name], respectively), the participant will be required to immediately discontinue the intervention.

12.2 Withdrawal Procedures:

As it is generally recommended that patients choosing to discontinue topiramate be weaned off of this medication, we will recommend for any participant choosing to withdraw from the study, or being withdrawn as described above, the following weaning schedule (consistent with clinical practice in the PWMC):

- Take 50 mg daily for one week, followed by:
- Take 25 mg daily for one week, and then discontinue.

In the event of an emergent medical situation, it may be recommended to cease topiramate without tapering the dose. For those participants that choose to withdraw, we will not plan to collect any additional data beyond that point, as the primary data of import in this study is topiramate concentration levels.

12.3 Termination Procedures:

It will be noted in the participant enrollment log that the participant has discontinued the study, and the date of the last study related visit. No additional data will be collected after that time. Data that has already been collected can be used in the study analysis.

Given the pragmatic nature of this study, including the fact that most participants recruited will be from our PWMCs and will continue to be followed through our PWMCs (if they so desire) after their participation in this study has terminated, many participants completing this study may continue to take topiramate after study completion. In that case, per usual clinical practice the medication will be prescribed by the participant's PWMC provider. For those not yet followed in the PWMC who are interested in continuing topiramate and/or being followed in our clinics, appointments in the PWMC will be established for continuation of topiramate and ongoing clinical management. All additional follow up in the PWMC will continue as per usual clinical

MEDICAL PROTOCOL (HRP-590)

PROTOCOL TITLE: Pharmacokinetics and Pharmacodynamics of Topiramate for Weight Loss in Youth: PHARMATOP

VERSION DATE: 05/03/2024

practice. If a participant elects to discontinue topiramate after study completion, we will use the same withdrawal procedure as described in **Section 12.2**, and additional topiramate will be provided by the IDS for this purpose.

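### The single weaning schedule in Section 12.2 doubles the dose of a participant who is taking 25 mg when they stop

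*Combined protocol and SAP*

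**What the plan says.** Section 12.2 explains that people stopping topiramate should generally be weaned off, and sets the scope of its schedule: "we will recommend for any participant choosing to withdraw from the study, or being withdrawn as described above, the following weaning schedule". The first step reads "Take 50 mg daily for one week, followed by"; the second step reads "Take 25 mg daily for one week, and then discontinue". The only exception in that section is: "In the event of an emergent medical situation, it may be recommended to cease topiramate without tapering the dose".

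Two other sections reuse the schedule without change. Section 12.3 applies it to completers who choose to stop, and on the drug supply for them it says "additional topiramate will be provided by the IDS for this purpose". Section 18.2 sends a participant with a serious adverse event judged related to topiramate or to study procedures through the same withdrawal procedure.

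Section 4.1 sets the doses a participant may be taking. Treatment starts at 25 mg daily, rises to 50 mg after one week and reaches 75 mg after two weeks. A participant who cannot tolerate escalation is reduced to 50 or 25 mg for the rest of the trial. In the earlier trial this happened to one of 30 participants. The protocol describes 75 mg as the dose used most often in the clinic.

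**The concern.** The schedule is a step-down from 75 mg, but its wording covers everyone. A participant on 25 mg who follows it goes up to 50 mg before coming down, which defeats the stated purpose of weaning. Those held at 25 mg are there because a higher dose was not tolerated. Those who leave in titration week 1 have not yet taken 50 mg in the study.

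The participants are aged 12 to under 18, and this is a direct dosing instruction. The safeguards are informal. Section 12.1 states "Participants will be allowed to withdraw from the study at any time" and "Those who wish to withdraw may notify the research team in writing or by telephone". The first scheduled medication review after baseline is the week 2 telephone call. Section 12.2 plans no further data collection for those who choose to withdraw, and Section 13.7 records new events only up to the last day of participation. A reaction that begins during the weaning weeks could therefore go unrecorded.

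**Working it through.** The plan contains no calculated figure to reproduce here. The check sets the schedule against each dose that Section 4.1 allows.

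**Step 1. Weaning dose relative to current dose** (Sections 12.2 and 4.1)

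| Current dose | Week 1 (50 mg) | Week 2 (25 mg) | Effect |
|---|---|---|---|
| 75 mg | 50/75 = 0.67 | 25/75 = 0.33 | Steps down |
| 50 mg | 50/50 = 1.00 | 25/50 = 0.50 | One extra week at the current dose, then down |
| 25 mg | 50/25 = 2.00 | 25/25 = 1.00 | Doubled, then back to the starting dose |

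**Step 2. Total drug over the two weeks, from 25 mg**

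- Schedule: 7 × 50 + 7 × 25 = 525 mg.
- Staying on 25 mg: 14 × 25 = 350 mg.
- Ratio: 525/350 = 1.5.

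**Step 3. Whether other text prevents it.** The emergency exception in Section 12.2 permits an untapered stop but does not address a routine exit at 25 mg. Section 13.2 stops treatment immediately in pregnancy, which takes that case out of the schedule. Section 12.1 requires immediate discontinuation after a related serious adverse event, yet Section 18.2 says that this discontinuation follows Section 12.2. Nothing makes the schedule depend on the current dose.

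**Step 4. How many participants.** Inputs: planned enrolment 65 (Section 10.1); dose reduction in 1 of 30 (Section 4.1); assumed drop-out 25%, with 10-15% described as usual (Section 15.2).

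- Expected number dose-reduced, 50 and 25 mg pooled: 65 × 1/30 = 2.17. The exact 95% interval for a rate of 1/30 is 0.1% to 17.2%, or about 0 to 11 of 65.
- The share of these on 25 mg is not given. Call it *s* and take 0, 0.5 and 1.
  - If all of them stop, completers included: *s* × 2.17 = 0, 1.08 or 2.17.
  - If 25% withdraw, independently of dose: *s* × 2.17 × 0.25 = 0, 0.27 or 0.54.
  - At 10% or 15% drop-out with *s* = 1: 0.22 or 0.33.
- Leavers in titration week 1, assuming drop-out spread evenly over 14 weeks: 65 × 0.25/14 = 1.16 at 25% drop-out, and 0.46 or 0.70 at 10% or 15%. The number is zero if nobody leaves in week 1 and higher if early exits cluster.

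**The case against.** The strongest reply is that the bullets should be read with their introduction. The section is about weaning, calls the schedule a recommendation and says it matches clinic practice. A sensible clinician would join it at or below the current dose. Study physicians prescribe, and the pharmacy keeps dispensing records for each participant (Section 4.2), so the current dose can be looked up. On this view the gap is a drafting omission for an unusual dose. That is a fair account of how it arose, and it lowers the chance that anyone is harmed. It does not change what the text tells staff and participants to do. Table 1 schedules dispensing only at baseline and week 8. If the baseline supply covers escalation to 75 mg, which the protocol does not state, an early leaver could already hold enough drug to take 50 mg without a new prescription.

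A second reply is that a week-1 leaver has not shown intolerance of 50 mg, which was the next planned dose. This stands: the tolerability argument applies only to those held at 25 mg. For the week-1 leaver the point is narrower, namely that a person who is stopping should not be told to take more.

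A third reply is that the counts rest on one event in 30, an unknown 25 mg share and assumed drop-out patterns, and that the case where everyone stops is unlikely because Section 12.3 expects many completers to continue. This also stands. The counts show only that the number is small.

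**Conclusion.** The instruction is wrong as written for a participant on 25 mg: followed literally, it doubles the dose for a week. That result is arithmetic on the protocol's own doses and needs no assumption. The schedule is correct from 75 mg and workable from 50 mg.

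The issue is a minor one of patient safety. It probably affects between none and about two of 65 participants through dose reduction, plus perhaps one who leaves in titration week 1. Those counts depend on the earlier 1-in-30 rate carrying over, on the unstated 25 mg share, on how many stop, and on evenly spread drop-out. The rate itself is imprecise, with an interval reaching about 11 of 65 for 50 and 25 mg combined. Clinical judgement may prevent the error, but the protocol does not require it. The point has no bearing on sample size, power or the primary analysis. It merits correction because the error is plain and the remedy is cheap.

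**What to change.** Amend Section 12.2 so that weaning starts at the next level below the current dose and no step exceeds the current dose:

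- From 75 mg: 50 mg for one week, 25 mg for one week, stop (unchanged).
- From 50 mg: 25 mg for one week, stop. This is a tidy-up; the present schedule is workable from 50 mg.
- From 25 mg: stop, or a step set by the medical monitor that is no higher than 25 mg. This is the essential change.

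Sections 12.3 and 18.2 then follow through their cross-references. The cost is one or two lines in an amendment and the matching participant instruction. Visits and exposure data are unchanged.

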Expectedness: The internal safety monitor will be responsible for determining whether an AE is expected or unexpected. An AE will be considered unexpected if the nature, severity, or frequency of the event is not consistent with the risk information previously described for the study intervention.

13.7 Time Period and Frequency for Event Assessment and Follow-Up:

All AEs will be captured on the appropriate case report form (CRF). Information to be collected includes event description, time of onset, clinician's assessment of severity, relationship to topiramate (assessed only by those with the training and authority to make a diagnosis), and time of resolution/stabilization of the event. All AEs occurring while in the study must be documented appropriately regardless of relationship. All AEs will be followed to adequate resolution.

Any medical condition that is present at the time that the participant is screened will be considered as baseline and not reported as an AE. However, if the study participant's condition deteriorates at any time during the study, it will be recorded as an AE.

The study staff will record all reportable events with start dates occurring any time after informed consent is obtained until the last day of study participation. As described in **Section**

MEDICAL PROTOCOL (HRP-590)

PROTOCOL TITLE: Pharmacokinetics and Pharmacodynamics of Topiramate for Weight Loss in Youth: PHARMATOP

VERSION DATE: 05/03/2024

5.1. at each study encounter study staff will inquire about the occurrence of AEs/SAEs since the last encounter. Events will be followed for outcome information until resolution or stabilization.

The PI will notify the IRB and external medical monitor ([name]) of any SAE that meets the definition of being an unanticipated problem that involves risk to subjects or others (UPIRTSO) within five days of knowledge of the event. The DSMB will be provided with AE and SAE information prior to their review of the study, at least every six months.

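### New adverse events that start during the study's recommended taper, or after an emergency stop, appear to fall outside the AE recording window, and no contact is scheduled then

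*Combined protocol and SAP*

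**What the plan says.** Section 12.2 recommends a step-down for anyone who withdraws or is withdrawn: one week at 50 mg, one week at 25 mg, then stop. In an emergency the drug may be stopped without a taper. For those who choose to leave, the section adds that "we will not plan to collect any additional data beyond that point, as the primary data of import in this study is topiramate concentration levels". Section 12.3 covers anyone who has discontinued. The log records the last study-related visit, and then "No additional data will be collected after that time". Neither section makes an exception for safety data.

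For completers, Section 12.3 says that "after their participation in this study has terminated, many participants completing this study may continue to take topiramate after study completion". It continues: "If a participant elects to discontinue topiramate after study completion, we will use the same withdrawal procedure", and "additional topiramate will be provided by the IDS for this purpose". Section 5.3 sets the study duration at 14 weeks.

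Section 13.7 limits recording to events with "start dates occurring any time after informed consent is obtained until the last day of study participation". It has staff ask about new events at each study encounter. For events already recorded it is firm: "All AEs will be followed to adequate resolution", and "Events will be followed for outcome information until resolution or stabilization". Table 1 schedules side-effect review at Weeks 2 and 4 by phone and at Weeks 6, 8, 10 and 14 at visits.

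**The concern.** The taper is a dosing period that the study itself recommends and, for completers, supplies. The participants are minors. AE capture under Section 13.7 needs two things: an onset date inside the window, and an encounter at which someone asks. During the taper the first is doubtful and the second is absent. The same holds after an abrupt stop, and that is where the seizure-precipitation risk listed in Section 13.1 applies.

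The internal medical monitor, the external monitor and the DSMB can review only what has been recorded. An event that first appears in those two weeks could go unseen by all three without any departure from the protocol.

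A second, smaller matter is that Sections 12.2 and 12.3 do not refer to Section 13.7, so the general data stop and the AE follow-up duty stand side by side with nothing to say which governs.

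**Working it through.** **1. Is the taper inside the onset window?**

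- Completers: Section 5.3 ends the study at Week 14. Section 12.3 speaks of participation having ended and puts the decision to stop the drug after study completion. The natural reading is that their taper begins after the last day of participation.
- Early leavers: Section 12.3 ties the data stop to the last study-related visit, and the Section 12.2 taper follows the exit. The natural reading is the same.
- Emergency stop: if the participant also leaves the study, there is no taper and the window closes at exit.
- Alternative reading: because the last day is undefined, the sponsor could count the taper as participation. New events would then qualify, but step 2 still applies.

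**2. Is there a contact at which they would be found?**

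- Taper length from 75 mg: 7 + 7 = 14 days. It is presumably shorter from a lower dose. Section 4.1 reports dose reduction in 1 of 30 in the earlier trial, and 1/30 x 65 = 2.2, so about 2 participants here.
- A completer who starts the taper at Week 14 takes the last dose at about Week 14 + 2 = Week 16.
- Scheduled AE contacts: Weeks 2, 4, 6, 8, 10 and 14 = 6. After Week 14 or after an earlier exit = 0.

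**3. How many people does this concern?**

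Inputs from Section 15.2: N = 65; usual drop-out 10% to 15%; planning value 25%; power text allows for 15. As a check on the plan's own figure, 50 / (1 - 0.25) = 66.7, so 67, close to the stated 65; and 15/65 = 23.1%.

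Drop-outs D:
- 0.10 x 65 = 6.5
- 0.15 x 65 = 9.75
- 0.25 x 65 = 16.25

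So about 7 to 16 leave early. The plan does not give the share s of completers who stop, so it is varied here from 0 to 1. Stoppers = D + s x (65 - D):

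| s (assumed) | D = 6.5 | D = 16.25 |
|---|---|---|
| 0 | 6.5 | 16.25 |
| 0.25 | 21.1 | 28.4 |
| 0.5 | 35.75 | 40.6 |
| 1 | 65 | 65 |

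These are participants who stop the drug, and so the number of calls a fix would need. The documents give no AE rate for a taper, so no count of missed events can be derived.

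**The case against.** The best reply is that Section 13.7 is the specific safety rule. It covers all AEs, has no carve-out for those who leave, and makes the time of resolution or stabilization a case report form item. Section 12.2 justifies its data stop by the importance of drug levels, which points to outcome data and not to safety. All of this stands for events already open at exit. A reader might infer that the plan forbids following those events. The documents do not support that: an event that starts on the last day can only be followed after exit, so staff would probably apply Section 13.7. For open events only a missing cross-reference remains. The reply does not help with events that first appear in the taper, because there Section 13.7 itself sets the limit.

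It can also be said that clinic care covers the gap. Most participants come from the weight management clinics, the principal investigator is a provider there, and appointments are offered to others who want them. Section 5.2 provides referral for disordered eating and for serious mood or suicidality findings. This softens the clinical risk. But clinic follow-up is at the participant's wish, and neither route is study AE capture.

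Three other inferences go too far:

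- That the taper exposes participants to seizures. The listed reaction concerns sudden withdrawal, which the taper is meant to avoid, and seizure disorder (other than febrile seizures) is an exclusion. The risk bears mainly on the abrupt stop.
- That related serious events are cut off by Section 12.3. Sections 12.1 and 18.2 require stopping the intervention, which is not necessarily leaving the study.
- That 7 to 16 participants have lost safety data. That range counts all drop-outs, including any already off drug, and its upper end uses a drop-out rate that the plan calls higher than usual.

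**Conclusion.** The point holds for new events. On the natural reading of Sections 5.3, 12.3 and 13.7, an adverse event that starts during a taper of up to 14 days, or after an emergency stop, is not recorded. If the taper is instead read as participation, there is still no scheduled contact to find it. For events open at exit the matter is one of clarification only.

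The conclusion rests on one reading of an undefined term, and that reading affects only the window; the absence of contacts comes straight from Table 1. The frequency of affected events is unknown. The consent pages are not in the file, so any terms there on safety contact after exit could not be checked. No primary or secondary objective, power or type I error is touched. Severity is minor.

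**What to change.** **Main change, Section 13.7.** Extend the AE onset window through the last taper dose, or through 14 days after the last dose when the drug is stopped without a taper (to match the taper length). Add one phone contact at that point for each participant who stops and has not withdrawn consent for it.

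**Clarification, Sections 12.2 and 12.3.** Limit the data stop to PK, efficacy and questionnaire data, and state that events open at exit are followed under Section 13.7 unless consent for this is withdrawn.

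**Cost.** Short wording changes in three sections, matching consent wording, and one call per stopper: about 7 to 16 for drop-outs, about 36 to 41 in total if half the completers also stop, and at most 65 if all do. No extra visits or blood draws.

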13.0 Risks to Participants

13.1 Foreseeable Risks:

Risks of blood sampling: There is a minimal risk of bruising, fainting, and infection associated with blood draws.

Risks of exposure to ionizing radiation: The iDXA scans involve exposure to a very low dose of ionizing radiation. The average amount of radiation that the average person would receive from the iDXA used in this study is less than 1% (0.01 mSv) of that received from natural sources of radiation by a Minnesota resident in one year (3 mSv).

Neuropsychological assessments (questionnaires): Potential risks related to the questionnaires include emotional distress related to thinking about and recording eating behavior symptoms, as well as possible “test fatigue.”

Risk from salivary collection (spitting into a tube or having saliva collected with a swab): There are no known health risks to participants related to the collection of saliva.

Personal Information: There is a risk that personal information could accidentally be released to someone other than study staff. We keep all personal information in computer databases protected by passwords or in locked file cabinets. Only study staff will have access to these documents and files. All individuals with the ability to access protected health data have completed HIPAA and Collaborative Institutional Training Initiative (CITI) training.

DNA/Genotyping: We are requesting consent to store and process DNA. We will be performing genotyping through the use of a genome-wide association (GWAS) chip. Results from a GWAS chip rarely imply much about an individual’s risk of disease. Rather, GWAS can identify regions of linkage disequilibrium containing potentially causal events. We will also be requesting consent for sequencing DNA. When this is done, it is similar to a fingerprint and is thus unique. All precautions will be taken to protect participant privacy and confidentiality. All genetic information will be stored in a secure database that is only labelled with an identification number. Only the investigators and the study team members will have access to this data as needed to carry out their study-related duties. DNA extraction, quantification, genotyping, and sequencing studies will be performed by the UMGC, which also has strict privacy rules in place to protect participant identity. Nevertheless, it is possible that someone in the future could identify a participant based on this unique genetic information. The DNA analysis will occur after all participant visits have occurred for the study. Any leftover saliva samples will be returned to the study team. The saliva sample collected can only be initially processed for approximately five years. Any saliva that remains after the sample is analyzed will be put back into storage indefinitely and may be used for future research projects. .

Expected Adverse Events – Topiramate: A majority of patients tolerate topiramate well and have no adverse events. Adverse events, if they do occur, are generally mild to moderate in intensity. The following have been identified as the most common potential adverse events related to topiramate: paresthesia (tingling in the hands, feet, and/or face), dysgeusia (altered or metallic

MEDICAL PROTOCOL (HRP-590)

PROTOCOL TITLE: Pharmacokinetics and Pharmacodynamics of Topiramate for Weight Loss in Youth: PHARMATOP

VERSION DATE: 05/03/2024

taste), fatigue, dizziness, somnolence, nervousness, psychomotor slowing, difficulty with memory and/or concentration/attention, cognitive problems, confusion, mood problems, fever, infection, and flushing. In our experience, the most common side effect is transient irritability and rarely do patients discontinue topiramate due to side effects. Of note, we will be following generative verbal fluency during the study with the COWA test and working memory via the NIH-TB List Sorting Working Memory Test and Pattern Comparison Processing Speed Test. According to the package insert, the following additional adverse reactions to topiramate have been identified:

- Acute myopia and secondary angle closure glaucoma
- Oligohidrosis and hyperthermia
- Metabolic acidosis
- Suicidal behavior and ideation. Participants who have active suicidal ideation will be referred to their own mental health provider, have a mental health referral generated or be referred to the emergency department.
- Fetal toxicity
- Kidney stones
- Seizure precipitation with sudden withdrawal
- Hyperammonemia and encephalopathy
- Hypothermia

13.2 Reproduction Risks:

Topiramate can cause fetal harm in pregnant women. Available data indicate an increased risk in oral clefts (cleft lip with or without cleft palate) with first trimester exposure to topiramate. When multiple species of pregnant animals received topiramate at clinically relevant doses, structural malformations, including craniofacial defects, and reduced fetal weights occurred in offspring. Therefore, all female participants who are sexually active must agree to use two forms of birth control during their time in the study. Females of childbearing potential will have pregnancy tests at baseline/screening (during which visit they also complete the iDXA scan) and at the Week 6, Week 10 and Week 14 visits. Urine pregnancy tests will be used as often as possible, but a serum pregnancy test may also be conducted. If a patient becomes pregnant while taking topiramate, treatment will be discontinued immediately and the patient will be apprised of the potential hazard to a fetus again at that time.

